#### 7.7.2 Physical Examination

Subjects will take a complete physical examination including a review of all body systems at the Screening Visit. On Day 0 visit, an assessment of general oral health by a dental professional will be conducted to assure compliance with relevant inclusion and exclusion criteria. Any abnormal findings at baseline will be recorded as medical history, and findings after baseline will be recorded as adverse events. No separate listing will be produced.

### 7.7.3 Vital Signs

Systolic (SBP), diastolic (DBP) blood pressure and heart rate will be measured, for all scheduled study visit days (Days 0, 3, 7, 14, 21 and 24), including Screening, in a seated position after at least 5 minutes of rest. Subjects with a systolic blood pressure ≥ 150 mmHg or a diastolic blood pressure ≥ 95 mmHg on Day 0 may be excluded from the study, as judged by the Investigator. The vital signs will be summarized by treatment and visit using the standard summary statistics (n, mean, SD, minimum, median and maximum) for mITT population. All data will also be listed by treatment, subject, visit and vital sign parameters.

#### 7.7.4 12-Lead Electrocardiogram

During the Screening Visit, a standard12-lead Electrocardiogram (ECG) will be obtained after the subject has rested in the supine position for at least 5 minutes. This assessment can be performed any time before blood sampling or at least 30 minutes after blood sampling, if applicable. Additionally, ECG will be measured on Day 7, Day 21 and Day 24 (if follow-up is required). ECG will be summarized by treatment and visit using the standard summary statistics (n, mean, SD, minimum, median and maximum) for the mITT population. All data will also be listed by treatment, subject, visit and ECG parameters. Overall assessment will be summarized using frequencies and percentage.

### 7.7.5 Clinical Laboratory

Serum chemistry, hematology and urinalysis will be measured in all subjects at Screening, Day 0 (baseline), Day 7 and Day 21. A drug screen will be conducted at Screening and Day 0. All clinical laboratory samples and urine samples for urinalysis will be analyzed at a central laboratory. The urine pregnancy test will be analyzed in the clinic. The Investigator will evaluate

17-May-2017 Final Version 1.0 Page 19 of 53

Sponsor Protocol No. 2016-NBTL-S-005

the clinical significance of each laboratory value outside of the reference range.

Each abnormal test will be evaluated as clinically significant or not clinically significant. All clinically significant abnormal laboratory values that represent an unexpected change from Baseline will be assessed as adverse events (AEs), and an AE eCRF must be completed.

Data in each of the three categories of hematology, chemistry and urinalysis will be listed by treatment, subject and parameter.

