No formal statistical comparisons between treatment groups will be conducted.
For other parameters, continuous data will be summarized using descriptive statistics (mean, standard deviation, minimum, maximum, median) to aid the data interpretation at each study visit:

Adverse events and other categorical variables will be tabulated by the number and % of subjects experiencing the event by treatment group. Other indicators will include severity, seriousness and relationship to study drug by treatment group. No formal statistical comparisons between treatment groups will be conducted. Recovery will be assessed by comparing OMI-20 total score, erythema subscore, ulcer subscore and all safety endpoints on Day 24 versus Day 21.
 Compliance Breath carbon monoxide levels will be presented by subject for each visit and will be used to identify concurrent smokers (CO > 10 ppm) and to stratify results of compliant and noncompliant subjects. Average number of lozenges used per day will be tabulated. Reasons for lozenge use of < 9 or > 20 lozenges per day will be collected at each visit and presented by treatment group and by visit.

LIST OF ABBREVIATIONS AND DEFINITIONS OF TERMS

Abbreviations	Term or Definition
°C	Celsius
°F	Fahrenheit
АСТН	Adrenocorticotropic hormone
ADL	Activities of Daily Living
AE	Adverse Event
BP	Blood Pressure
CFB	Change from baseline
CFR	Code of Federal Regulations
cm	Centimeters
СО	Carbon Monoxide
CTCAE	Common Terminology Criteria for Adverse Events
DBP	Diastolic Blood Pressure
ECG	Electrocardiogram
EOT	End of Treatment
eCRF	Electronic Case Report Form
EDC	Electronic Data Capture
ePDAT®	Electronic Patient Data Acquisition Tablet
GCP	Good Clinical Practice
GSK	GlaxoSmithKline
IB	Investigators Brochure
ICF	Informed Consent Form
ICH	International Conference on Harmonization
IND	Investigational New Drug Application
IRB	Institutional Review Board
kg	Kilograms
L	Liters
mg	Milligrams
mITT	Modified-intent-to-treat
NCI	National Cancer Institute
NRT	Nicotine Replacement Therapy
OMI	Oral Mucositis Index

Randomized, Parallel Group, Assessor-Blind Comparative Study-Oral Mucosal Effects Niconovum USA, Inc.

OTC	Over the counter
рН	A measure of the acidity or alkalinity of a solution
PI	Principal Investigator
PP	Per protocol
ppm	Parts-per-million
RAISC	RAI Services Company
RAI	Reynolds American Inc.
RBC	Red blood cell count
Rx	Prescription
SAE	Serious Adverse Event
SAP	Statistical Analysis Plan
SBP	Systolic Blood Pressure

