 Assessment of lozenge use will be collected through the ePDAT® system (once daily) and take-home journals.

 Biopsy will only be performed in the case of suspicious lesions as determined by oral examinations through a second opinion by a dentist or dental surgeon. Each lesion will be biopsied once.

 Clinically significant abnormalities at Study Day 21 will be re-evaluated at Day 24 for recovery.

Sponsor Protocol No. 2016-NBTL-S-005

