## 5.4 Safety Endpoints

- Clinical laboratory assessments (clinical chemistry; hematology; serology; urinalysis)
- Vital signs
- 12-lead Electrocardiogram (ECG)
- Analysis of biopsied materials (if any) and adverse events

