## 7.7 Safety Analyses

Safety data in this study are comprised of adverse events, physical examination, vital signs and clinical laboratory assessment. All safety data will be analyzed using the mITT Population.

The continuous type safety endpoints will be summarized by treatment using descriptive statistics (n, mean, SD, median, minimum, maximum) for mITT population. The categorical type safety endpoints will be summarized by treatment using frequency and percentage for mITT population. No formal inferential tests will be performed on safety data.

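### SAP Section 7.7.5 plans only listings for laboratory data, although Section 7.7 requires safety endpoints to be summarised by treatment

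*SAP*

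**What the plan says.** SAP Section 5.4 names clinical laboratory assessments among the safety endpoints. Section 7.7 treats them the same way: "Safety data in this study are comprised of adverse events, physical examination, vital signs and clinical laboratory assessment". It then sets the general rule, "The continuous type safety endpoints will be summarized by treatment using descriptive statistics", for the mITT population, and asks for frequencies and percentages by treatment for categorical safety endpoints. Section 6.1 also says that safety endpoints are to be summarised in the mITT population. The protocol synopsis, under Statistical Methods, says "For other parameters, continuous data will be summarized using descriptive statistics" and refers to each study visit.

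Section 7.7.5 gives the laboratory schedule: "Serum chemistry, hematology and urinalysis will be measured in all subjects at Screening, Day 0 (baseline), Day 7 and Day 21". Its one sentence on presentation is "Data in each of the three categories of hematology, chemistry and urinalysis will be listed by treatment, subject and parameter". The table list in the SAP contents has vital signs (14.3.4), ECG (14.3.5.x), carbon monoxide and lozenge use (14.3.6.x) and recovery of OMI-20 scores (14.3.7.x), but no laboratory table. Listing 16.2.8.X is the only output for the three panels.

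The neighbouring sections are fuller. Section 7.7.3 says "The vital signs will be summarized by treatment and visit using the standard summary statistics" and also lists the data. Section 7.7.4 does the same for ECG. In Table 1 (Section 2.4), the Day 24 entry for vital signs carries footnote 11: "Clinically significant abnormalities at Study Day 21 will be re-evaluated at Day 24 for recovery".

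**The concern.** Safety and tolerability is the secondary objective, and laboratory data are one of its main systemic measures. A programmer who follows Section 7.7.5 and the table list will produce no laboratory mean, change or shift by arm.

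One by-arm route remains, through the adverse event tables, and it is narrow. Under Section 7.7.5 the investigator judges the clinical significance of values outside the reference range, and only clinically significant values that are an unexpected change from baseline become adverse events. Section 7.8 states that investigators and study staff are not blinded to treatment. A drift in one arm that stays inside the reference range, or is judged not clinically significant, would appear in no table. What does appear would have passed through a judgement made with knowledge of the arm.

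Section 1 of the SAP also states that its analysis methods do not deviate from the protocol, which is hard to square with a listing-only plan for this domain.

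**Working it through.** The plan gives no figure to reproduce. It is descriptive, with no significance level (Section 6.5) and no sample size calculation (Section 3.3). The main check sets the passages side by side.

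**Step 1. Presentation by domain**

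| Domain | Listed | Summary by arm | Change from baseline by arm | Agrees with Section 7.7? |
|---|---|---|---|---|
| Laboratory (7.7.5, Listing 16.2.8.X) | yes | no | no | no |
| Vital signs (7.7.3, Table 14.3.4) | yes | yes, by visit | no | yes |
| ECG (7.7.4, Tables 14.3.5.1 and 14.3.5.2) | yes | yes, by visit | no | yes |
| Adverse events (7.7.1, Tables 14.3.1.1 to 14.3.1.3) | yes | yes | not applicable | yes |

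Only the laboratory row fails the SAP's own rule. Change from baseline is defined as an endpoint only for OMI-20, so its absence from the vital-sign and ECG rows breaks no rule.

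**Step 2. Is the listing a stated exception?** Section 7.3 says outright that concomitant medication will have no summary table. Section 7.7.5 makes no such statement, so the conflict with Section 7.7 is left open.

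**Step 3. Amount of data affected.** Inputs: 100 subjects (Section 3.3); four collections, at Screening and Days 0, 7 and 21 (Section 7.7.5); three panels.

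- Per panel: 100 × 4 = 400 subject-visits.
- Over three panels: 3 × 400 = 1,200.
- During treatment (Days 7 and 21): 100 × 2 = 200 per panel.

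These are maxima, reached if every subject attends every visit.

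**Step 4. What change from Day 0 would add for vital signs.** Section 6.4.2 leaves missing values unreplaced, so a Day 0 mean and a Day 21 mean may come from different subjects. A change uses the same subjects at both visits. Whether it is also more precise depends on the within-subject correlation ρ, which the documents do not give. Assuming equal SD at both visits and 50 per arm:

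- SD of change / SD of raw value = √(2(1 − ρ)).
- 95% half-width of a between-arm difference in raw visit means = 1.96 × √(2/50) = 0.392 SD. For mean change, multiply by the ratio above.

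| ρ (assumed) | SD ratio | Half-width, raw (SD) | Half-width, change (SD) |
|---|---|---|---|
| 0.3 | 1.183 | 0.392 | 0.464 |
| 0.5 | 1.000 | 0.392 | 0.392 |
| 0.7 | 0.775 | 0.392 | 0.304 |
| 0.8 | 0.632 | 0.392 | 0.248 |

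Change is more precise only above ρ = 0.5. The half-widths only gauge noise; the plan reports no inferential statistics and none are proposed here.

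**Step 5. Vital signs on Day 24.** The text of Section 2.4 has vital signs taken at each visit, and Section 7.7.3 names Day 24. Table 1 attaches footnote 11, on re-evaluating Day 21 abnormalities, to that same entry. Section 7.7.6 speaks of re-evaluating safety endpoints that were clinically significantly abnormal on Day 21. Table 14.3.4 continues to an EOS row without saying who contributes to it.

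**The case against.** The best defence is that Sections 7.7 and 7.7.5 can be read together. Section 7.7.5 never says that the data will only be listed; it sits under Section 7.7, which supplies the summary, and Section 8 warns that the shells may not cover every aspect of the study. On that reading the missing table is an oversight, and the general rule still applies. This stands as far as intent goes: a reader might infer from the contrast with the vital-sign and ECG sections that summaries were dropped on purpose, but the documents do not show it. It does not remove the inconsistency. The gap is in the text of Section 7.7.5 as well as in the shells, and neither specifies a laboratory summary.

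A second defence is that other by-arm safety information exists. It does: vital signs and ECG are tabulated by arm and visit, and adverse events by arm. A reader might infer that no systemic safety change could be seen by arm, and that would be wrong. By-arm vital-sign means at Day 0 and later visits show approximate movement, exact when the same subjects contribute. None of this substitutes for a laboratory summary.

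The protocol is weaker support than the SAP. Its sentence on other continuous data does not mention treatment group, and the text after its closing colon is not in the supplied copy. The explicit by-treatment rule for continuous safety data is in SAP Section 7.7.

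For Day 24, a reader might infer that footnote 11 limits vital signs to subjects who were abnormal on Day 21. The footnote does not say so, and two other passages point to every subject. Elsewhere the SAP is explicit when a Day 24 measurement is conditional, as it is for ECG.

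**Conclusion.** The inconsistency is established for laboratory data. Section 7.7.5 and the table list provide listings only for hematology, chemistry and urinalysis, against Sections 7.7 and 6.1, and they do not match the protocol's per-visit summary of other continuous parameters. Up to 400 subject-visits per panel would have no by-arm statistic, assuming full attendance. Laboratory changes would reach a by-arm table only through adverse event reporting by unblinded staff. The point should be corrected because it concerns the secondary objective; it does not touch the primary endpoint.

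It goes no further than that. The vital-sign plan meets the SAP's rules, and the lack of change from Day 0 there is a weakness of presentation. The gain from adding it is that the same subjects are compared at both visits. A gain in precision requires a within-subject correlation above 0.5, and the documents give neither that correlation nor an expected dropout rate. Day 24 vital signs are a separate and smaller matter of unclear text.

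**What to change.** - **Section 7.7.5 (the correction).** Replace the listing sentence with one saying that the three panels will be summarised by treatment and visit for the mITT population (value and change from Day 0 for continuous results, frequency and percentage for categorical results) and also listed. Add the matching laboratory table and a low/normal/high shift table from Day 0 to Days 7 and 21. The listing shell already holds the values and a reference-range indicator.
- **Listing 16.2.8.X.** Add a visit column, and replace the Full Analysis Set label, which names a population that Section 4 does not define.
- **Table 14.3.4 (an improvement).** Add change-from-Day-0 rows, each using subjects measured at both visits.
- **Day 24 vital signs.** Reconcile Section 7.7.3 with the footnote 11 marker in Table 1, and state who contributes to the EOS row.

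The cost is some SAP wording and a few extra standard tables. No new data are needed.

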### 7.7.6 Recovery

Recovery will be assessed by comparing OMI-20 total score, erythema subscore, and ulcer subscore at Day 24 with those at Day 21. Other safety endpoints with clinically significant abnormal values at Day 21 will be re-evaluated on Day 24 to assess recovery from Day 21.

Difference between Day 21 and Day 24 in OMI-total score, erythema subscore and ulcer subscore will be summarized using descriptive statistics (mean, standard deviation, minimum, maximum, and median) and presented by treatment group using the mITT population and subpopulations. No inferential statistical comparisons between groups will be conducted.

## 7.8 Analysis Prior to Study Completion

An early statistical analysis of data of administrative type is planned for this study following completion of the 60th randomized subject and prior to the completion of full study with 100 randomized subjects and hard lock of the clinical database. This statistical analysis provides with only descriptive summaries and without any confirmatory type of analysis using statistical significance. This will provide an initial evaluation of selected study results and an assessment of adequacy of the result outputs for the final study report.

The study is blinded only to the extent that the dental hygienist evaluating the oral health of subjects does not know to which treatment group the subjects have been assigned. Otherwise the study could be considered an open label study as the subjects, investigators, and study staff are not blinded to the treatment. The individual dental hygienist evaluating the oral health of subjects will not be informed of the results of this pre-planned analysis prior to the completion of the full study analysis. The study will continue to recruit and randomize beyond 60 subjects until the protocol specified 100 randomized subjects are evaluated. Also, the results of the completed study will be presented in the final report, only descriptively.

17-May-2017 Final Version 1.0 Page 20 of 53

Sponsor Protocol No. 2016-NBTL-S-005

## 8 TABLES, LISTINGS AND GRAPHS (TLGs) SHELLS

The following TL shells are provided as a framework for the display of data from this study. The shells may change due to unforeseen circumstances. These shells may not be reflective of every aspect of this study but are intended to show the general layout of the Tables and Listings that will be included in the final report. Table headers, variables names and footnotes will be modified as needed following data analyses.

17-May-2017 Final Version 1.0 Page 21 of 53

Table 14.1.1 Disposition of Subjects and Analysis Sets

	Nicotine Polacrilex n (%)	Nicotine Bitartrate n (%)	Overall n (%)
Number of Subjects in Randomized Population	XX	XX	XX
Number of Subjects in Modified Intent-to-Treat Population	XX	XX	XX
Number of Subjects in Per Protocol Population	XX	XX	XX
Number of Subjects in Heavy Lozenge Use Population	XX	XX	XX
Number of Subjects in Concomitant Smoker Population	XX	XX	XX
Number (%) of Subjects who Completed the Study	xx (xx.x%)	xx (xx.x%)	xx (xx.x%)
Number (%) of Subjects who Discontinued Early	xx (xx.x%)	xx (xx.x%)	xx (xx.x%)
Reasons for Early Discontinuation			
Adverse Event	xx (xx.x%)	xx (xx.x%)	xx (xx.x%)
Physician Decision	xx (xx.x%)	xx (xx.x%)	xx (xx.x%)
Protocol Deviation	xx (xx.x%)	xx (xx.x%)	xx (xx.x%)
Sponsor's Decision	xx (xx.x%)	xx (xx.x%)	xx (xx.x%)
Subject Non-compliance	xx (xx.x%)	xx (xx.x%)	xx (xx.x%)
Withdrawal by Subject	xx (xx.x%)	xx (xx.x%)	xx (xx.x%)

Note: Percentages are calculated based on the number of subjects in the Randomized Population per treatment and overall.

Data Source: Listing 16.2.1

17-May-2017 Final Version 1.0 Page 22 of 53

Table 14.1.2 Demographics and Baseline Characteristics
Modified Intent-to-Treat Population

	Nicotine Polacrilex	Nicotine Bitartrate	Overall
	(N=xx)	(N=xx)	(N=xx)
Age (years)*			
n	xx	XX	XX
Mean	xx.x	xx.x	XX.X
SD	xx.xx	xx.xx	XX.XX
Minimum	xx	xx	XX
Median	xx	xx	XX
Maximum	XX	XX	XX
Sex, n (%)			
n	xx	xx	XX
Male	xx (xx.x%)	xx (xx.x%)	xx (xx.x%)
Female	xx (xx.x%)	xx (xx.x%)	xx (xx.x%)

Note: \*Age at Informed Consent

Percentages are calculated based on the number of subjects in the ITT Population per treatment and overall.

Data Source: Listing 16.2.4.1, Listing 16.2.4.2

Programming Note: Table will also include race, ethnicity, height (cm), weight (kg), BMI (kg/m²)

17-May-2017 Final Version 1.0 Page 23 of 53

Table 14.1.3 Summary of Tobacco Use History Modified Intent-to-Treat Population

Product	Categories	Nicotine Polacrilex (N=xx)	Nicotine Bitartrate (N=xx)	Overall (N=xx)
Cigarettes	Duration (Years)			
	n	XX	XX	XX
	Mean	XX.XXX	XX.XXX	XX.XXX
	SD	XX.XXXX	XX.XXXX	XX.XXXX
	Minimum	XX.XX	XX.XX	XX.XX
	Median	XX.XXX	XX.XXX	XX.XXX
	Maximum	XX.XX	XX.XX	XX.XX
	Cigarettes (Per Day)			
	n	XX	XX	XX
	Mean	XX.X	XX.X	XX.X
	SD	XX.XX	XX.XX	XX.XX
	Minimum	XX	XX	XX
	Median	XX.X	XX.X	XX.X
	Maximum	xx	xx	xx
	Frequency			
	≥ 30 cigarettes/day	xx (xx.x%)	xx (xx.x%)	xx (xx.x%)
	20 - 29 cigarettes/day	xx (xx.x%)	xx (xx.x%)	xx (xx.x%)
	< 20 cigarettes/day	xx (xx.x%)	xx (xx.x%)	xx (xx.x%)

Data Source: Listing 16.2.4.9

17-May-2017 Final Version 1.0 Page 24 of 53

Table 14.2.2.1 Summary of Change from Baseline in OMI-20 Total Score Modified Intent-to-Treat Population

		Treatment	
	Statistics	Nicotine Polacrilex	Nicotine Bitartrate
Baseline	n	XX	xx
	Mean ± SD	$xx.x \pm x.xx$	$xx.x \pm x.xx$
	Median	xx.x	XX.X
	Min, Max	xx, xx	XX, XX
Day 3	n	xx	XX
	Mean ± SD	$xx.x \pm x.xx$	$xx.x \pm x.xx$
	Median	xx.x	XX.X
	Min, Max	xx, xx	XX, XX
hange from baseline to Day 3	n	xx	XX
	Mean ± SD	$xx.x \pm x.xx$	$xx.x \pm x.xx$
	Median	XX.X	XX.X
	Min, Max	xx, xx	XX, XX
Day 7	n	xx	XX
	Mean ± SD	$xx.x \pm x.xx$	$xx.x \pm x.xx$
	Median	XX.X	XX.X
	Min, Max	xx, xx	xx, xx
Change from baseline to Day 7	n	XX	xx
	Mean ± SD	$xx.x \pm x.xx$	$xx.x \pm x.xx$
	Median	xx.x	XX.X
	Min, Max	xx, xx	xx, xx

Note: OMI – Oral Mucositis Index Data Source: Listing 16.2.6.1

<Programming Note: continue for Day 14 and Day 21.>

17-May-2017 Final Version 1.0 Page 25 of 53

Similar tables as 14.2.2.1 will be generated for:

- Table 14.2.2.2 Summary of Change from Baseline in OMI-20 Total Score Per-Protocol Population
- Table 14.2.2.3 Summary of Change from Baseline in OMI-20 Total Score
  Heavy Lozenge Use Population
- Table 14.2.2.4 Summary of Change from Baseline in OMI-20 Total Score Concomitant Smoker Population
- Table 14.2.3.1 Summary of Change from Baseline in OMI Erythema Score Modified Intent-to-Treat Population
- Table 14.2.3.2 Summary of Change from Baseline in OMI Erythema Score Per-Protocol Population
- Table 14.2.3.3 Summary of Change from Baseline in OMI Erythema Score Heavy Lozenge Use Population
- Table 14.2.3.4 Summary of Change from Baseline in OMI Erythema Score Concomitant Smoker Population
  - Table 14.2.4.1 Summary of Change from Baseline in OMI Ulcer Score Modified Intent-to-Treat Population
  - Table 14.2.4.2 Summary of Change from Baseline in OMI Ulcer Score Per-Protocol Population
  - Table 14.2.4.3 Summary of Change from Baseline in OMI Ulcer Score
    Heavy Lozenge Use Population
  - Table 14.2.4.4 Summary of Change from Baseline in OMI Ulcer Score Concomitant Smoker Population

17-May-2017 Final Version 1.0 Page 26 of 53

Table 14.3.1.1 Overall Summary of Treatment Emergent Adverse Events (TEAEs)

Modified Intent-to-Treat Population

	All Adverse Events		
	Nicotine Polacrilex (N=xx)	Nicotine Bitartrate (N=xx)	
Number (%) of Subjects with TEAE	xx (xx.x%) [xx]	xx (xx.x%) [xx]	
Number (%) of Subjects with Serious TEAE	xx (xx.x%) [xx]	xx (xx.x%) [xx]	
Number (%) of Subjects with Severe TEAE	xx (xx.x%) [xx]	xx (xx.x%) [xx]	
Number (%) of Subjects with Related TEAE	xx (xx.x%) [xx]	xx (xx.x%) [xx]	
Number (%) of Subjects with Study Discontinued Due to TEAE	xx (xx.x%) [xx]	xx (xx.x%) [xx]	

Note: An AE is considered to be related if it is possibly or probably related to study processes.

Summaries are presented as: number of subjects, (percentage of subjects), and [number of events].

Data Source: Listing 16.2.7

17-May-2017 Final Version 1.0 Page 27 of 53

Table 14.3.1.2 Summary of Treatment Emergent Adverse Events by System Organ Class and Preferred Term Modified Intent-to-Treat Population

	All Adverse Events		
System Organ Class/	Nicotine Polacrilex	Nicotine Bitartrate	
Preferred Term	(N=xx)	(N=xx)	
Any System Organ Class			
Any Event	xx (xx.x%) [xx]	xx (xx.x%) [xx]	
Cardiac Disorders	xx (xx.x%) [xx]	xx (xx.x%) [xx]	
Any Event	xx (xx.x%) [xx]	xx (xx.x%) [xx]	
Bradycardia	xx (xx.x%) [xx]	xx (xx.x%) [xx]	

Note: All adverse events recorded throughout the study are summarized by treatment and MedDRA System Organ Class and Preferred Term.

Summaries are presented as: number of subjects, (percentage of subjects), and [number of events]. If multiple events occur in a category, it will be counted only once for calculation of frequencies at subject level.

Data Source: Listing 16.2.7

17-May-2017 Final Version 1.0 Page 28 of 53

Table 14.3.1.3 Treatment-Emergent Adverse Events by System Organ Class, Preferred Term and Maximum Relationship (Modified Intent-to-Treat Population)

		All Adverse Events		
System Organ Class/	Maximum	Nicotine Polacrilex	Nicotine Bitartrate	
Preferred Term	Relationship	(N=xx)	(N=xx)	
ny System Organ Class				
Any Event	Unlikely	xx (xx.x%) [xx]	xx (xx.x%) [xx]	
	Possible	xx (xx.x%) [xx]	xx (xx.x%) [xx]	
	Probably	xx (xx.x%) [xx]	xx (xx.x%) [xx]	
ardiac Disorders				
Any Event	Unlikely	xx (xx.x%) [xx]	xx (xx.x%) [xx]	
	Possible	xx (xx.x%) [xx]	xx (xx.x%) [xx]	
	Probably	xx (xx.x%) [xx]	xx (xx.x%) [xx]	

Note: All adverse events recorded throughout the study are summarized by treatment and MedDRA System Organ Class and Preferred Term.

Summaries are presented as: number of subjects, (percentage of subjects), and [number of events]. If multiple events occur in a category, it will be counted only once for calculation of frequencies at subject level.

Data Source: Listing 16.2.7

17-May-2017 Final Version 1.0 Page 29 of 53

Table 14.3.4 Summary of Vital Signs Modified Intent-to-Treat Population

Parameter (Unit)	Visit	Statistic	Nicotine Polacrilex (N=xx)	Nicotine Bitartrate (N=xx)
Systolic Blood Pressure (mmHg)	Screening			
		n	xx	XX
		Mean	xx.x	XX.X
		SD	xx.xx	XX.XX
		Minimum	xx	XX
		Median	xx.x	XX.X
		Maximum	xx	XX
	Day 0 Baseline			
	Day 3			

Note: EOS=End of Study, ET=Early Termination

Data Source: Listing 16.2.9

Programming Note: Parameter also includes Diastolic Blood Pressure (mmHg), Pulse Rate (bpm), Programming will continue for Day 7, 14, 21

and EOS.

17-May-2017 Final Version 1.0 Page 30 of 53

Table 14.3.5.1 Summary of Overall ECG Interpretation Modified Intent-to-Treat Population

Visit		Nicotine Polacrilex (N=xx)	Nicotine Bitartrate (N=xx)
Baseline		(14-22)	(14-22)
Daseille			
	n	XX	XX
	Normal, n (%)	xx (xx.x%)	xx (xx.x%)
	Abnormal, Not Clinically Significant, n (%)	xx (xx.x%)	xx (xx.x%)
	Abnormal, Clinically Significant, n (%)	xx (xx.x%)	xx (xx.x%)
Day 7			
	n	XX	xx
	Normal, n (%)	xx (xx.x%)	xx (xx.x%)
	Abnormal, Not Clinically Significant, n (%)	xx (xx.x%)	xx (xx.x%)
	Abnormal, Clinically Significant, n (%)	xx (xx.x%)	xx (xx.x%)

Note: EOS=End of Study

Data Source: Listing 16.2.10

Programming Note: Programming will continue for Day 14, 21 and EOS/ET.

17-May-2017 Final Version 1.0 Page 31 of 53

Table 14.3.5.2 Summary of ECG Continuous Data Safety Population

			,	
ECG Parameters		•	Nicotine Polacrilex	Nicotine Bitartrate
(unit)	Visit	Statistics	(N=xx)	(N=xx)
Ventricular Rate (bpm)	Baseline*			
		n	xx	XX
		Mean	XX.X	XX.X
		SD	XX.XX	xx.xx
		Minimum	xx	xx
		Median	xx.x	XX.X
		Maximum	XX	XX
	Day 7			
		n	xx	XX
		mean	XX.X	XX.X
			xx.x	XX.X
		XX	xx	XX

Note: \*Baseline is defined as the last observation prior to the dose.

<ECG Parameter (unit)> = Ventricular Rate (bpm), PR Interval (msec), QRS Duration (msec), QT Interval (msec), QTcB Interval (msec)

Programming Note: Table also includes Day 14, 21 and EOS/ET.

17-May-2017 Final Version 1.0 Page 32 of 53

Table 14.3.6.1 Summary of Breath carbon monoxide (CO) levels (mITT Population)

			Treatment	
Visit		Statistics	Nicotine Polacrilex	Nicotine Bitartrate
Day 3	Average CO level (Compliant)	n	XX	XX
		Mean ± SD	$xx.x \pm x.xx$	$xx.x \pm x.xx$
		Median	xx.x	XX.X
		Min, Max	xx, xx	xx, xx
	CO level <=10pmm or not?	n (%)		
	Yes		xx (xx.x%)	xx (xx.x%)
	No		xx (xx.x%)	xx (xx.x%)

Day 7

Day 14

Day 21

Data Source: Listing 16.2.5.1

17-May-2017 Final Version 1.0 Page 33 of 53

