### 2 INTRODUCTION TO THE STUDY

## 2.1 Overview of Study

This will be a single-center, ambulatory, randomized, parallel group, assessor-blind, 3-week, safety study in healthy adults motivated to quit smoking. Subjects will be instructed to quit smoking (starting Day 1) and use 9 - 20 lozenges per day for 3 weeks. Subjects will be randomized 1:1 to treatment with Nicotine Bitartrate 4 mg mint lozenge (test product) or Nicorette® [Nicotine Polacrilex] 4 mg mint lozenge (reference product). In each treatment group a minimum of 10% of the study population will be smokers of  $\geq$  30 cigarettes/day, and a minimum of 40% of the study population will be smokers of 20 - 29 cigarettes/day. Randomization will be stratified by smoking status so that the treatment assignment is balanced within smoking status.

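### Bazett's QTcB is the only rate-corrected QT in the ECG table, although quitting and the start of lozenge use fall between the baseline and on-treatment ECGs; adding QTcF would be a free, minor improvement.

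*SAP*

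**What the plan says.** The note to SAP Table 14.3.5.2 gives the full list of continuous ECG parameters: "Ventricular Rate (bpm), PR Interval (msec), QRS Duration (msec), QT Interval (msec), QTcB Interval (msec"). The QT entries are "QT Interval (msec), QTcB Interval (msec"), so QTcB is the only corrected interval. SAP 7.7.4 plans summaries by treatment and visit and a listing of all ECG data by subject, but names no correction formula.

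On timing:

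- The same table note states: "Baseline is defined as the last observation prior to the dose".
- SAP 7.7.4 places the first ECG at Screening ("During the Screening Visit, a standard12-lead Electrocardiogram (ECG) will be obtained") and then adds: "ECG will be measured on Day 7, Day 21 and Day 24 (if follow-up is required"). SAP Table 1 has no ECG on Day 0, so the last pre-dose ECG is the Screening ECG, from Day -21 to Day -1.
- SAP 2.1 states: "Subjects will be instructed to quit smoking (starting Day 1) and use 9 - 20 lozenges per day for 3 weeks". The notes to Table 1 put the first lozenge on the same day as quitting, Day 1.

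The 12-lead ECG is a named safety endpoint (SAP 5.4). SAP 7.7 excludes inferential tests on safety data, and the supplied documents set no QTc threshold or outlier category.

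**The concern.** A corrected QT is meant to allow comparison of ECGs recorded at different heart rates. Here the source of nicotine changes, from cigarettes to lozenges, between baseline and every on-treatment ECG, so a systematic change in rate over that interval is possible. The ECG conditions that SAP 7.7.4 and Table 1 set are supine rest and timing relative to blood sampling. The supplied text does not fix the timing relative to the last cigarette or lozenge.

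Bazett divides QT by the square root of RR. If QT varies with RR less steeply than a square root, QTcB falls when rate falls, even with no change in repolarisation. That is the unhelpful direction for a safety measure, because it offsets a true increase. A rise in rate does the opposite and produces an apparent increase. What is at stake is how the within-arm change from baseline in one descriptive safety table is read.

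**Working it through.** The plan states no QT, heart-rate or power figure on this point, so there is none to reproduce. The check asks how far QTcB moves from rate alone.

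**Inputs from the SAP.** Bazett is the only correction (Table 14.3.5.2). Baseline is the Screening ECG (Table 14.3.5.2 note with Table 1). Quit day and first lozenge are Day 1, in both arms. On-treatment ECGs are on Days 7 and 21.

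**Assumptions, not in the documents.** QT at 60 bpm (Q60) is 400 ms. Baseline rate is 75 bpm. Rate falls by 3, 5, 7 or 10 bpm. The true relation is QT = Q60 × RR^b, with RR = 60/HR and b between 1/3 (Fridericia exact) and 0.50 (Bazett exact).

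**Formula.** QTcB = QT / RR^0.5 = Q60 × RR^(b - 0.5).

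**Step 1: b = 1/3.** QTcB = 400 × (HR/60)^(1/6).

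- 75 bpm: 415.2 ms
- 72 bpm: 412.3 ms, change -2.8
- 70 bpm: 410.4 ms, change -4.7
- 68 bpm: 408.4 ms, change -6.7
- 65 bpm: 405.4 ms, change -9.8
- 80 bpm (a 5 bpm rise): 419.6 ms, change +4.5

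**Step 2: other exponents.** Change in QTcB (ms) from 75 bpm, rate effect only:

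| b | fall of 3 bpm | fall of 10 bpm |
|---|---|---|
| 1/3 | -2.8 | -9.8 |
| 0.37 | -2.2 | -7.6 |
| 0.40 | -1.7 | -5.8 |
| 0.50 | 0 | 0 |

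With no change in rate every entry is 0. With b = 1/3, Q60 of 400 or 420 ms and a baseline rate of 70 to 80 bpm, falls of 3 to 10 bpm give -2.7 to -10.9 ms.

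**Step 3: masking.** With b = 1/3, add a true increase d to Q60: change in QTcB = (400 + d) × (HR/60)^(1/6) - 415.2.

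| true increase | fall of 3 | fall of 5 | fall of 7 | fall of 10 bpm |
|---|---|---|---|---|
| +5 ms | +2.3 | +0.4 | -1.6 | -4.7 |
| +10 ms | +7.5 | +5.5 | +3.5 | +0.3 |

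**Step 4: between arms.** With b = 1/3, after a common 7 bpm fall, the QTcB difference between arms is 0 if both shift equally. It is about -1.0, -2.0 and -3.1 ms if one arm falls a further 1, 2 or 3 bpm.

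**Step 5: what the planned rows would show.** A simulation of 200,000 subjects used b = 1/3, mean rate 75 bpm (SD 10), a mean fall of 7 bpm (SD 6), QTcF 400 ms (SD 18) and a true mean increase of 5 ms (SD 8). Mean uncorrected QT rose by 18.0 ms and mean QTcB fell by 1.8 ms. Applying Fridericia to the group mean QT and group mean rate gave about +6.0 ms.

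**Step 6: the alternative under the same test.** QTcF = QT / RR^(1/3) = Q60 × RR^(b - 1/3). Its rate artefact is 0 at b = 1/3. At b = 0.40 a 10 bpm fall moves it from 394.1 to 397.9 ms (+3.8, against -5.8 for QTcB). At b = 0.50 it moves from 385.4 to 394.7 ms (+9.3, against 0). The two corrections depend on rate about equally at b = (1/3 + 1/2)/2 = 5/12, about 0.417. Below that value QTcF depends on rate less.

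**The case against.** The strongest reply is that the size is entirely assumed. No document gives a heart rate, an expected shift or its direction. Nicotine continues at 9 to 20 lozenges a day, and the mITT population keeps subjects who go on smoking. The largest figures also need an exponent near 1/3. All of this stands, and it is why the result is stated as a range that includes zero.

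A reader might infer that the table will conceal QT prolongation. The documents do not support that. Ventricular rate and uncorrected QT are summarised beside QTcB, so a rate fall would be visible, and Step 5 shows that the tabulated means allow an approximate cross-check. SAP 7.7.4 promises subject-level values, from which QTcF could be derived. Table 14.3.5.1 separately reports the overall ECG interpretation. These mitigations are real but incomplete. In Step 5 uncorrected QT and QTcB move in opposite directions, and the only corrected row has the wrong sign. The shell shows no change-from-baseline rows. Table 14.3.5.1 cites a Listing 16.2.10, but the listing shells end at 16.2.9. A later derivation would also be a post hoc choice of formula.

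A reader might also infer a bias between products. Both arms have the same quit instruction and a 4 mg nicotine lozenge under 1:1 randomisation, so a common shift largely cancels, and nothing supplied says that the two lozenges affect heart rate differently.

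Two limits of the record also stand. SAP section 8 says that the shells may change, and the supplied protocol text has no ECG methods section, so the statement that Bazett is the only correction applies to the SAP.

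**Conclusion.** The point holds in a limited, conditional form. The SAP plans one rate correction, and the change from cigarettes to lozenges separates the baseline ECG from the on-treatment ECGs. If heart rate falls over that interval and the true exponent is below 0.50, QTcB drops from rate alone and can partly mask a within-arm increase. The size runs from 0 to about -10 ms under the main assumptions (Q60 400 ms, 75 bpm, falls of up to 10 bpm), and to about -11 ms at the extreme tried.

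The problem concerns change from baseline within an arm, much more than test versus reference. QTcB feeds no decision rule, and the primary OMI-20 analysis is unaffected. This is a minor improvement to a descriptive safety table. No planned analysis fails because of it.

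**What to change.** In SAP 7.7.4 and Table 14.3.5.2:

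1. Add QTcF = QT / RR^(1/3), with RR = 60 / ventricular rate in bpm, computed for each subject at each ECG.
2. Show per-subject change from baseline by visit for QTcF, using the existing baseline definition.
3. State before database lock that QTcF is the main QTc summary, and keep QTcB as a supporting row. Step 6 is the reason to keep both: agreement between them is reassuring, and disagreement points to a rate effect.

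The cost is one derived variable and a few table rows. QT and ventricular rate are already among the table's parameters, so no new ECGs or data are needed.

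Three related shell details can be settled in the same edit: the population in the table title (Safety Population) is not defined in SAP section 4, the programming note asks for a Day 14 ECG that Table 1 does not schedule, and the ECG listing needs a shell.
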